## Summary of Changes

Version 2	Added new source for $^{68}\text{Ga}$ -NeoBOMB1
-----------	---

## PROTOCOL SYNOPSIS

TITLE	 Ga-NeoBOMB1 and  Ga-PSMA R2 PET/MRI in Patients with Biochemically Recurrent Prostate Cancer and Non-Contributory Conventional Imaging
STUDY PHASE	Phase II
INDICATION	Prostate cancer
INVESTIGATIONAL PRODUCT OR PROCEDURE	 Ga-NeoBOMB1  Ga-PSMA R2
PRIMARY OBJECTIVE(S)	To evaluate  Ga-NeoBOMB1 PET/MRI and  Ga-PSMA R2 PET/MRI for detection of recurrent prostate cancer after initial therapy in patients with biochemical recurrence
SAMPLE SIZE	50 participants
STATISTICAL CONSIDERATIONS	Prospective single center, single-arm study.

## SCHEMA

## LIST OF ABBREVIATIONS AND DEFINITION OF TERMS

BPH	Benign prostatic hyperplasia
Ga-68	Gallium-68
GRPR	Gastrin releasing peptide receptor
IRB	Institutional Review Board
IV	Intravenous
PC	Prostate cancer
PET/MRI	Positron emission tomography – magnetic resonance imaging
PSA	Prostate-specific antigen
PSMA	Prostate specific membrane antigen
SUV	Standardized Uptake Value
TRUS	Transrectal ultrasound

## 1. OBJECTIVE

### Specific Aim

To evaluate  $^{68}\text{Ga}$ -NeoBOMB1 and  $^{68}\text{Ga}$ -PSMA R2 PET/MRI for detection of recurrent prostate cancer after initial therapy in patients meeting the criterion of biochemical recurrence.

## 2. BACKGROUND

### 2.1 Preliminary information

Data from the American Cancer Society suggests that prostate cancer (PC) will continue to be the leading non-cutaneous cancer diagnosis in males in 2016 in the US with 180,980 estimated new cases, and has the second highest mortality with 26,120 estimated deaths (1). Subsequent treatment is multifaceted and may involve observation, surgery (prostatectomy), radiation therapy (external beam or brachytherapy), hormonal therapy, chemotherapy, or a combination of these (2-4).

Up to 40% of the patients with prostate cancer develop biochemical recurrence within 10 years after initial treatment (5). Usually an increase of the PSA-level precedes a clinically detectable recurrence by months to years (6). However, it cannot differentiate between local, regional or systemic disease with the necessary precision that is essential for further disease management (7).

Morphological imaging methods exhibit considerable limitations: sensitivity ranges between 25% and 54% for the detection of local recurrence by transrectal ultrasound (TRUS) or contrast-enhanced CT and is moderately improved by using functional MRI techniques (7-9). The sensitivity for detection of lymph node metastases of CT or MRI is reported to be 30-80% (10). Ultra-small particles of iron oxides (USPIOs) proved to be very effective, but are yet to be approved by regulatory authorities (11). Bone metastases presenting as osteoblastic lesions can be effectively detected by bone scintigraphy, PET, CT and MRI (12,13).

Various targets have been addressed by molecular imaging to improve the detection of recurrent prostate cancer. PET tracers such as  $^{18}\text{F}$ - or  $^{11}\text{C}$ -labeled choline and  $^{11}\text{C}$ -acetate have been investigated for the diagnosis of recurrent (14-16) prostate cancer. Their feasibility in primary diagnosis is limited because of uptake in benign tissue such as benign prostatic hyperplasia (BPH) or inflammatory lymph nodes (17,18). In addition, fluorinated versions are not available in the United States, while  $^{11}\text{C}$ -labeled tracers cannot be widely used due to the requirement for an on-site cyclotron due to the short half-life.  $^{18}\text{F}$ -FACBC, a new synthetic amino acid, might be superior when compared to  $^{11}\text{C}$ -choline PET/CT (19). However, recent work indicates that  $^{18}\text{F}$ -FACBC uptake in prostate cancer is similar to that in BPH nodules (20). Prostate-specific membrane antigen (PSMA) continues to elicit high interest. This cell surface protein is significantly overexpressed in prostate cancer cells when compared to other PSMA-expressing tissues such as kidney, proximal small intestine or salivary glands. It therefore provides a promising target for prostate cancer-specific imaging.

Recently methods have been developed to label PSMA ligands with  $^{68}\text{Ga}$  and  $^{18}\text{F}$ . Initial experience suggests that these novel tracers can detect prostate cancer relapses and

metastases with high contrast by binding to the extracellular domain of PSMA, followed by internalization (21,22). However, these promising agents do not detect all recurrences.

Consequently, improved imaging of biochemically recurrent prostate cancer continues to be an area of unmet clinical need.

Gastrin-releasing peptide receptors (GRPR) are highly overexpressed in several human tumors, including PC (23). GRP receptor was detected in 63-100 % of human prostate cancer tissue (24,25). Moreover, because of their low expression in BPH and inflammatory prostatic tissues (25), imaging of GRPR has potential advantages over current choline- and acetate-based radiotracers.

Maina and colleagues evaluated Ga-SB3 in 8 patients with breast cancer and 9 patients with prostate cancer. All patients had disseminated disease and had received previous therapies (26). Ga-SB3 did not produce adverse effects and identified cancer lesions in 4 out of 8 (50 %) with breast cancer and 5 out of 9 (55 %) with PC. An improved version of this radiopharmaceutical, Ga-NeoBOMB1, is showing promising results in preliminary studies (27,28). Ga-NeoBOMB1 has undergone extensive pre-clinical testing confirming specific and high affinity GRPR targeting (IC50: 1-2 nM), both in vitro and in vivo, as well as an appropriate pharmacokinetic profile compatible with a diagnostic use and a favorable safety profile. Ga-NeoBOMB1 specifically and strongly bound on the cell-membrane of PC-3 cells displaying low internalization, as expected for receptor antagonists. During a translational study in prostate cancer patients Ga-NeoBOMB1 rapidly localized in pathological lesions achieving high contrast imaging (29).

A phase 1-2 clinical study (MITIGATE trial) aimed to evaluate Ga-NeoBOMB1 safety, tolerability, biodistribution, dosimetry and preliminary diagnostic performance is ongoing in GIST patients at Innsbruck University. The safety assessment on the first 6 patients enrolled in the study confirmed good tolerance, with no AEs reported. Uptake in tumors was fast with good visibility of the metastasis already at 1h after administration, associated with rapid renal and blood clearance (30).

PET/MRI is an advanced multimodality technology that can provide both biological and morphological information of various biological processes. Compared to PET/CT, simultaneous PET/MRI has advantages resulting from reduction in the radiation exposure and improvements in diagnostic ability due to better soft tissue contrast (31).

## **2.2 Study Agent**

We will use Ga-NeoBOMB1 and Ga-PSMA R2 as the PET radiopharmaceuticals. These are not FDA-approved products, but we have letters of cross-reference for FDA-approved INDs allowing the use of these tracers in this proposed clinical indication under a Stanford investigator sponsored IND (████████).

## **2.3 Clinicaltrials.gov**

Since Ga-NeoBOMB1 and Ga-PSMA R2 are not FDA-approved products, we will register the study on clinicaltrials.gov once initial FDA, IRB and SRC approvals are in place.

## **2.4 Rationale**

In this study, we propose to use a well-established PET isotope, Gallium-68 (Ga), bound to a bombesin receptor antagonist, NeoBOMB1, which has high affinity for gastrin-releasing peptide receptors (GRPR), and to PSMA R2 which has high affinity for prostate specific

[figure not shown]
membrane antigen (PSMA). GRPR proteins are highly overexpressed in several human tumors, including prostate cancer (23) and its overexpression has been demonstrated in patients with biochemically recurrent prostate cancer (32,33). Therefore, imaging GRPR has the potential to improve the lesion detection in prostate cancer.

Ga and F labeled PSMA ligands can detect prostate cancer relapses and metastases with high contrast by binding to the extracellular domain of PSMA, followed by internalization (21,22).

Therefore, we propose the following aim:

[figure not shown]
- To evaluate Ga-NeoBOMB1 and Ga-PSMA R2 PET/MRI for detection of recurrent prostate cancer after initial therapy in patients with biochemical recurrence.

### **Imaging prostate specific membrane antigen using Ga-PSMA R2**

Prostate specific membrane antigen (PSMA) is a type II integral membrane glycoprotein identified on human prostatic carcinoma cell lines. The PSMA protein has a unique 3-part structure consisting in a 19-amino-acid internal portion, a 24-amino-acid transmembrane portion, and a 707-amino-acid external portion. The PSMA gene is located on the short arm of chromosome 11 in a region that is not commonly deleted in prostate cancer. PSMA triggers a signal that allows internalization of the protein on the cell surface into an endosomal compartment. This characteristic seems to be useful for diagnostic and therapeutic (theragnostic) approach in which PSMA could be used as an antigenic target or as a specific docking-station for tailored small molecules (34).

Increased PSMA expression has been detected most notably in prostate cancer; though, it was also detected in the peritumoral and endotumoral capillaries of a variety of malignancies including renal cell carcinomas, transitional cell carcinomas, and colon carcinomas (35). Nearly all adenocarcinomas of the prostate demonstrate PSMA expression in most primary and metastatic lesions (36). Immuno-histochemical studies have shown that PSMA expression increases in cases of de-differentiated, metastatic, or hormone-refractory disease (37) and its expression level is a significant prognosticator for disease outcome (38).

Several urea-based PSMA ligands have already been successfully tested in prostate cancer patients confirming good imaging performance and favorable safety profile. In line with existing guidelines, the diagnostic doses of the Ga-PSMA ligands range 120-200 MBq/patient (approximately 2 to 3 MBq/kg). Considering the half-life of Ga, as well as the foreseen imaging and blood sampling schedule in early phase trials (up to ¾ h for imaging acquisition or 6h for PK sampling), a dose of 3 MBq/kg, but not less than 150 MBq and not more than 250 MBq, is considered adequate to obtain good quality imaging using Ga-PSMA R2. The proposed dose is also consistent with the one applied in the two marketed AAA diagnostic products Somakit and NETSpot.

The safety of the cold compound present in a single dose of Ga-PSMA R2 is supported by the preclinical data obtained in GLP single and repeated dose toxicity studies performed in rats and mini-pigs showing good tolerability of the compound and no toxicity signs at the highest tested dose (in single dose studies: 8000 (rats) and 3500 (mini-pigs) times the maximum foreseen human dose; in repeated dose studies: 2600 (rats) and 1150 (mini-pigs) times the maximum foreseen human dose). Similarly, no adverse effects have been observed in the safety pharmacology studies performed in rats and mini-pigs at any of the tested doses which were 4000 (studies on effects on CNS and respiratory function in rats) or 1150 times higher (study on effects on cardiovascular function in mini-pigs) than the dose foreseen in human for the imaging drug product.

## 2.5 Study Design

This is a prospective, single center, single-arm phase II study enrolling 50 participants with biochemically recurrent prostate cancer. All patients will first be seen by a Stanford Cancer Institute physician and then referred if appropriate on clinical grounds to [name] or his colleagues for this study. Eligible participants will undergo baseline assessments at enrollment. The following steps will take place after the participant has signed the written consent (participants will be randomized to have  $^{68}\text{Ga}$ -NeoBOMB1 first followed by  $^{68}\text{Ga}$ -PSMA R2 within 2 weeks or  $^{68}\text{Ga}$ -PSMA R2 first followed by  $^{68}\text{Ga}$ -NeoBOMB1 within 2 weeks [50/50 chance for each schedule]).

1. Participant will be asked to drink 1 to 2 glasses of water before arrival at the clinic
2. Participants will be weighed and vital signs (heart rate, blood pressure, respiratory rate, pulse oxymetry) will be recorded
3. Participant will be injected IV with 150 to 250 MBq of  $^{68}\text{Ga}$ -NeoBOMB1
4. Vital signs (heart rate, blood pressure, respiratory rate, pulse oxymetry) will be recorded after the injection
5. Participant will void immediately prior to the scan
6. Approximately 45 minutes after the radiopharmaceutical IV administration, data acquisition will begin in the pelvic region and move toward the head. First, localizer MRI scans will be performed to define the table positions. After correct positioning of the spatial acquisition windows is ensured, the combined PET/MRI acquisition will be initiated with 3 to 5 table positions at a 4-min acquisition time per table position.
7. Participants will be given a copy of the consent form s/he signed and will be dismissed.
8. Vital signs (heart rate, blood pressure, respiratory rate, pulse oxymetry) will be recorded again at the completion of the study
9. Participants will be contacted at 24 to 72 hours following the scan in order to capture potential occurring Adverse Events.

The same will be repeated for  $^{68}\text{Ga}$ -PSMA R2 (within 2 weeks of  $^{68}\text{Ga}$ -NeoBOMB1):

1. Participant will be asked to drink 1 to 2 glasses of water before arrival at the clinic
2. Participants will be weighed and vital signs (heart rate, blood pressure, respiratory rate, pulse oxymetry) will be recorded
3. Participant will be injected IV with 150 to 250 MBq of  $^{68}\text{Ga}$ -PSMA R2
4. Vital signs (heart rate, blood pressure, respiratory rate, pulse oxymetry) will be recorded after the injection
5. Participant will void immediately prior to the scan
6. Approximately 45 to 60 minutes after the radiopharmaceutical IV administration, data acquisition will begin in the pelvic region and move toward the head. First, localizer MRI scans will be performed to define the table positions. After correct positioning of the spatial acquisition windows is ensured, the combined PET/MRI acquisition will be initiated with 3 to 5 table positions at a 4-min acquisition time per table position. Only MR sequences required for attenuation correction of PET data will be acquired.
7. Participants will be given a copy of the consent form s/he signed and will be dismissed.
8. Vital signs (heart rate, blood pressure, respiratory rate, pulse oxymetry) will be recorded again at the completion of the study
9. Participants will be contacted at 24 to 72 hours following the scan in order to capture potential occurring Adverse Events.

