### **5.2 Details of Imaging (ie, dynamic, static, number of scans, etc.)**

A localizer MRI scan will be performed at 45 minutes after injection of 150 to 250 MBq of Ga-NeoBOMB1 (or Ga-PSMA R2, depending on randomization) to define the table positions. After correct positioning of the spatial acquisition windows is ensured, the combined PET/MRI acquisition will be initiated with 3–5 table positions at a 4-min acquisition time per table position. A volumetric T1 acquisition with fat-water separation and motion correction to enable free-breathing will be obtained at each table position and used for the generation of attenuation maps and for anatomic allocation of the PET results. Simultaneously with the start of the T1 MRI sequence, the PET acquisition will start at the same table position, thus ensuring optimal temporal and regional correspondence between MRI and PET data. The PET acquisition time will be 4 min per table position, taking delayed acquisition times and radioactive decay into account. As the T1 will take less than 4\ minutes, a rapid diffusion weighted MRI will also be performed. After completion of the PET acquisition, the table will be moved to the next table position and the procedure will be repeated. Upon completion of the PET acquisition for all stations, volumetric post-contrast T1- and T2-weighted MR images may be obtained at multiple stations as needed.

A localizer MRI scan will be performed at 45 minutes after injection of 150 – 250 MBq of Ga-PSMA R2 (or Ga-NeoBOMB1, depending on randomization) to define the table positions. After correct positioning of the spatial acquisition windows is ensured, the combined PET/MRI acquisition will be initiated with 3–5 table positions at a 4-min acquisition time per table position. ----Only MR sequences required for attenuation correction of PET data will be acquired.

Participants will be randomized to have Ga-NeoBOMB1 first followed by Ga-PSMA R2 within 2 weeks or Ga-PSMA R2 first followed by Ga-NeoBOMB1 within 2 weeks (50/50 chance for each schedule).

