### **11.3 Interim analyses**

We will evaluate if Ga-NeoBOMB1 and Ga-PSMA R2 will have the same findings as what was noted with Ga68 PSMA-11 and Ga68 RM2 (bombesin), ie, about 2/3 same findings, while 1/3 will show different findings. We will do the interim analysis after enrollment of 20 participants. If all participants will have the same findings or if one

radiopharmaceutical will outperform the other (no additional lesions found by one vs another), the study will be discontinued.

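### Section 2.5 ties the attenuation-only MR to the PSMA R2 scan while 5.2 implies scan order; followed literally, 2.5 confounds tracer with MR content in the tracer comparison

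*Combined protocol and SAP*

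**What the plan says.** **Section 2.5** states the 1:1 randomised order and then lists the steps by tracer. Step 6 of the NeoBOMB1 list begins "Approximately 45 minutes after the radiopharmaceutical IV administration" and places no limit on MR sequences. The next list opens with "The same will be repeated for" and names PSMA R2. Its step 6 begins "Approximately 45 to 60 minutes after the radiopharmaceutical IV administration" and ends "Only MR sequences required for attenuation correction of PET data will be acquired".

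**Section 5.2** has two paragraphs, each open to either tracer.
- The first covers NeoBOMB1, or "Ga-PSMA R2, depending on randomization) to define the table positions". It includes a volumetric T1 at each table position, used for attenuation maps and anatomic allocation. It adds that "a rapid diffusion weighted MRI will also be performed", and makes post-contrast T1 and T2 optional.
- The second names PSMA R2 first and NeoBOMB1 as the alternative, again "depending on randomization) to define the table positions". It allows attenuation-correction sequences only.
- Both paragraphs give 45 minutes.

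**Section 6.2** sends the reader to 2.5 for image collection.

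**Use of the comparison.** The primary outcome in 10.1 compares lesion counts on NeoBOMB1 PET/MRI, PSMA R2 PET/MRI and MR, reported per patient for each method. Section 11.3 looks at 20 participants and stops the study if all have the same findings or if one "radiopharmaceutical will outperform the other (no additional lesions found by one vs another), the study will be discontinued".

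**Reading rules.** Section 11.4 calls tracer positivity on uptake against adjacent background and gives MRI its own criterion based on diffusion, T1w and T2w images. Section 10.2 has PET read blinded to other studies and MR read blinded to PET. Section 11.1 has MRI and PET/MRI evaluated separately. Section 5.3 has the PET/MRI scans interpreted by consensus and each lesion tabulated.

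**The concern.** The two sections use different rules for which scan gets the reduced MR: the tracer in 2.5, and by implication the scan order in 5.2. If staff follow 2.5 as written, every NeoBOMB1 scan may carry diagnostic MR and no PSMA R2 scan does. Randomising which tracer comes first balances order effects but leaves this difference in place, because the MR content moves with the tracer.

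Any help that diffusion or T2w images give a PET/MRI reader, for example in deciding whether faint uptake is a lesion, would then count for one tracer only. The comparison is more than a tabulation, since it feeds the primary outcome and can end the study at 20 participants. The uptake window is a second difference by tracer that appears in 2.5 and not in 5.2.

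**Working it through.** **1. The passages side by side**

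| | 2.5 | 5.2 |
|---|---|---|
| Scans identified by | tracer | paragraph, either tracer by randomization |
| Fuller MR | NeoBOMB1 list (no restriction) | first paragraph |
| Attenuation-only MR | PSMA R2 list | second paragraph |
| Start after injection | about 45 min NeoBOMB1; about 45 to 60 min PSMA R2 | 45 min for both |

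Section 5.2 never uses the words first or second scan. That reading comes from its paragraph order and the reference to randomization. Under 5.2 a participant's two scans still differ in MR content, but over the 1:1 randomization the difference falls equally on both tracers.

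**2. What the plan quantifies.** It gives no figure for the effect of MR content on PET/MRI lesion counts. The 90% power in 11.5 concerns PET against MR, and this point does not rest on it. What follows is therefore an illustration.

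**3. Interim illustration**

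Inputs from 11.3: n = 20, and about 1/3 of findings differing between tracers.

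Assumptions:
- The 1/3 applies per participant and splits equally: a = b = 1/6, where a is the probability that only NeoBOMB1 shows an extra lesion and b the same for PSMA R2.
- A share f of a tracer's extra findings is lost when its scan has reduced MR. Findings seen on both scans are left unchanged.
- The study stops if either tracer shows no extra lesion in any of the 20. This includes the case where all findings are the same.

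P(stop) = (1−a)^20 + (1−b)^20 − (1−a−b)^20.

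*No loss (f = 0):* (5/6)^20 = 0.0261 and (2/3)^20 = 0.0003, so P(stop) = 0.0261 + 0.0261 − 0.0003 = 0.0519.

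*Reduced MR follows PSMA R2 (2.5 literally):* replace b by b(1−f). At f = 0.5, b becomes 1/12. Then (11/12)^20 = 0.1755 and (3/4)^20 = 0.0032, so P(stop) = 0.0261 + 0.1755 − 0.0032 = 0.1984.

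*Reduced MR follows scan order (5.2), 10 participants per order:* each tracer shows nothing extra with probability (1−b(1−f))^10 × (1−b)^10. At f = 0.5 this is (11/12)^10 × (5/6)^10 = 0.06766, so P(stop) = 2 × 0.06766 − 0.00317 = 0.1321.

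| f | 2.5: P(stop) | 2.5: PSMA R2 adds nothing | 2.5: NeoBOMB1 adds nothing | 5.2: P(stop) | 5.2: each tracer adds nothing |
|---|---|---|---|---|---|
| 0 | 0.0519 | 0.0261 | 0.0261 | 0.0519 | 0.0261 |
| 0.2 | 0.0824 | 0.0572 | 0.0261 | 0.0764 | 0.0386 |
| 0.3 | 0.1085 | 0.0837 | 0.0261 | 0.0921 | 0.0467 |
| 0.5 | 0.1984 | 0.1755 | 0.0261 | 0.1321 | 0.0677 |

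The extra chance of stopping from tying MR to tracer rather than to order is the difference between the two P(stop) columns: 0, 0.0060, 0.0164 and 0.0663.

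**The case against.** **The sections may be compatible.** Section 2.5 gives NeoBOMB1 first and then PSMA R2 within two weeks of it, so its attenuation-only scan is also the second scan of that schedule. Section 5.2, the dedicated imaging section, may simply generalise this. The reading is fair and cannot be excluded. It does not settle the matter, because 2.5 states both orders before listing steps by tracer, its uptake windows also differ by tracer, and 6.2 sends staff to 2.5.

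**The reading rules may already remove the bias.** Calling positivity on uptake (11.4) with PET and MR read blinded to each other (10.2) would leave little or no effect. This is the strongest objection, and it is why the size may be zero. What it leaves open is 5.3, where PET/MRI scans are interpreted with no statement on whether the reader sees same-session diffusion or T2w images.

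**The contrast in MR content may be modest.** Post-contrast T1 and T2 are optional, and the volumetric T1 itself supplies the attenuation maps. The difference may be mainly the diffusion images. That stands too.

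**Stronger readings.** A reader might infer that two tracers with identical PET findings would be stopped wrongly because MR adds lesions to one. The documents do not support this: 11.3 already stops the study when all findings are the same, so in that case MR content would change only the stated reason. A reader might also combine the sensitivities in 11.5 into a read that counts a lesion if either PET or MR shows it. No section describes such a read.

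**Conclusion.** The wording conflict is real and the passages must be reconciled. Followed literally, 2.5 aliases tracer with MR content in every participant, in the counts used by 10.1 and 11.3, and randomised order does not break the link.

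The size is unknown and may be near zero. In the illustration, as f goes from 0 to 0.5, the chance of stopping rises from 5.2% to 19.8% if reduced MR follows PSMA R2, against 13.2% at f = 0.5 if it follows scan order. The asymmetry is the main statistical point. Under 2.5 the chance that PSMA R2 appears to add nothing goes from 2.6% to 17.5%, while NeoBOMB1 stays at 2.6%. Under 5.2 both tracers move together, to 6.8% each. These figures rest on a per-participant reading of the 1/3, an equal split and an assumed f.

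The documents do not show that the trial will be confounded. They permit it, and the correction is cheap enough to make.

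**What to change.** - **2.5 and 5.2:** give one rule for MR content that does not depend on tracer, and say explicitly in 5.2 whether the two paragraphs mean first and second scan. Reconcile the stated uptake windows.
- **5.3 and 11.4:** state that both tracers' PET images are read with the same MR input, either attenuation MR only or the participant's one full MR for both. If the full MR is used, align the blinding wording in 10.2. This instruction is needed even if 5.2 is adopted, because a participant's two scans would still differ in MR content.
- **Comparator:** state that the participant's one full MR, read alone, is the MR comparator for both tracers.

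The cost is wording and a reading instruction. No extra scans or readers are needed.
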